**Aim 2. To determine the individual differences in cognitive processes that moderate behavioural change in older adults.** We hypothesize that individual differences in cognitive processes moderate behaviour change in older adults. Therefore, we will test the extent to which differences in adaptive decision-making (i.e., reward-effort computations) and dimensional measures of motivational traits (i.e., grit and growth mindset) moderate the effects of the intervention on change in physical activity. We will capture individual differences in motivation to exert effort for rewards using the Effort Expenditure for Rewards Task (EEfRT): This is an established computerized cognitive paradigm that maps onto the reward valuation/effort construct in the Research Domain Criteria (RDoC) framework. This approach will provide a novel, mechanistic understanding of how dimensional constructs of motivation influence adaptive decision-making and behavioural change.

**Aim 3: To define brain markers that predict successful real-world behavioural change in aging.** We will test the hypothesis that successful behavioural change (i.e., increased physical activity post-intervention versus baseline) is associated with enhanced activation of self-referential (i.e., ventromedial prefrontal cortex) and reward valuation (i.e., ventral striatum, ventral tegmental area) brain networks as indexed by task-based and resting-state fMRI. Acquisition of baseline brain imaging data will allow us to ask whether and what neuromarkers predict successful behavioural change as a function of the intervention.

The hypotheses that will be investigated in this study are:

- (1) Social-Motivation combined with self-transcendence messaging will increase physical activity in older adults, compared to an active control condition.
- (2) Enhanced brain network modularity at baseline will predict exercise-related executive function gains.
- (3) Individual differences in structural and functional network connectivity at baseline will predict change in physical activity.

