To test our main hypothesis that social motivation + self-transcendence messaging + home-based physical training will produce the largest increase in physical activity over the course of the 4-week intervention compared to the active control, we will perform repeated measures ANCOVAs (with group as a between-subject factor and pre-post session as a within-subject factor). This hypothesis will be examined by analyzing total number of steps and percent time sedentary. We will analyze structural/functional MRI connectivity to test the hypothesis that increased physical activity following the intervention is associated with enhanced brain connectivity between brain regions in reward valuation (i.e., ventral tegmental area and ventral striatum) and social processing (vmPFC). We will conduct seed-based functional connectivity analyses using methods as in our prior research [9, 29-31]. To mitigate the influence of motion, we will identify and address artifactual motion outliers in data modeling, and employ quality assurance software to mitigate head motion artifacts and physiological aliasing ([https://www.nitrc.org/projects/artifact\\_detect](https://www.nitrc.org/projects/artifact_detect)). We will control for the effects of demographic variables (e.g., age, sex, education, diet, mood, socioeconomic status, alcohol, vascular risk factors and sleep). We apply a whole-brain height threshold of  $p < 0.001$  ( $T = 3.24$ ) and false discovery rate cluster threshold of  $p < 0.05$ . We will examine brain modularity, which indexes the segregation between networks, and has previously been shown to predict cognitive gains after a physical exercise intervention [20]. In addition to these hypothesis-driven analyses, we will perform an agnostic, data driven multi-voxel pattern analysis of resting-state data using an approach published by our collaborator [21].

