Analyses on the resting state and task-based fMRI analyses are considered secondary. Briefly they will be modeled using the general linear model approach. First-level analyses will include all necessary nuisance regressors to minimize motion artifacts influence, spatial smoothing kernel and high pass filtering, as well as physiological aliasing for the low-frequency fluctuations in resting state data. To answer questions about the intervention effect and prediction of behavioural change, both a priori ROI seed-based analyses of functional connectivity are performed as well as data-driven whole-brain multi-voxel pattern analysis, modularity analyses and graph theory per several previous publications using data-driven approaches to predict clinical outcomes. Besides the primary outcomes, adherence and drop-outs are also included in the prediction model as outcome variables, to examine what individual characteristics affect participation in the current intervention. Robust-prediction models of MRI data and psychosocial measures will be generated using cross-validation methods to improve the generalization of the results.

Selection bias will also be considered in our study by comparing characteristics between the source population (i.e., PREVENT-AD participants) and the study sample. For eligible participants invited to participate in the study, we will document the proportion of those who decline and agree to participate. We will compare demographic information (age, sex, education, ethnicity, socioeconomic status, smoking status, and self-reported physical activity) between those who agree and those who refuse to participate using t-tests and chi-square tests of independence. Multivariate logistic regression models will be used to determine whether these characteristics are associated with acceptance relative to refusal to participate in the study.

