Aim 3) To identify the individual differences and brain fingerprint that predict successful behavior change at the single subject level in older adults at risk for AD, we will analyze baseline behavioral and MRI data gathered during the intervention in addition to already acquired longitudinal multimodal brain and behavioral data. We will use both a-priori regions of interest (ROIs) vmPFC and salience network seed-based analyses of brain connectivity as well as data-driven whole brain multivariate pattern analyses per previous publications using data-driven approaches to predict clinical outcomes. We will apply rigorous machine-learning methods and independent linear regression models using leave-one-out cross validation (LOOCV) and bootstrap resampling to identify the brain networks that predict treatment response (physical activity engagement) at an individual level. We use methods that we published in a similar sample size of older adults. This approach will provide solid mechanistic insight into the brain basis of successful behavior change. We expect these results to be generalizable and yield single subject values.

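### The a-priori brain regions for the secondary imaging aim differ between protocol and SAP, and no main seed or contrast is named

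*SAP*

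**What the plan says.** - **Protocol section 2, Aim 3.** Successful behaviour change is expected to be linked to greater activity in these networks: "self-referential (i.e., ventromedial prefrontal cortex) and reward valuation (i.e., ventral striatum, ventral tegmental area) brain networks as indexed by task-based and resting-state fMRI".
- **Protocol section 6b.** The connectivity hypothesis is that increased physical activity goes with "enhanced brain connectivity between brain regions in reward valuation (i.e., ventral tegmental area and ventral striatum) and social processing (vmPFC"). The section describes these analyses as hypothesis-driven and sets them apart from a data-driven pattern analysis.
- **Protocol section 6b, later.** Imaging analyses are classed as secondary. The text says that "both a priori ROI seed-based analyses of functional connectivity are performed" but does not name the regions there.
- **SAP Aim 3.** "We will use both a-priori regions of interest (ROIs) vmPFC and salience network seed-based analyses of brain connectivity". The ventral striatum and VTA appear nowhere in the SAP, and the salience network appears nowhere in the protocol.
- **Error control.** Only protocol section 6b gives an imaging threshold. For voxels: "We apply a whole-brain height threshold of" p < 0.001 (T = 3.24). For clusters: "and false discovery rate cluster threshold of" p < 0.05. The SAP gives none.

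Neither document says which one governs, names a main seed or contrast, sets an order of testing, or gives a rule across seeds.

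**The concern.** An analysis is a priori only if the list of regions was fixed beforehand. Here there are two lists, with one region in common. An analyst cannot work from the SAP alone, because the threshold is only in the protocol, so both lists are live.

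The protocol says that the brain imaging has already been collected under the parent cohort. The written region list is therefore the main safeguard against settling on a seed after the results are known. With two lists and no main test, a finding in the ventral striatum, the VTA or the salience network can be matched to one document and presented as planned, although the other document does not support it. The threshold does not guard against this, because it works inside a single map and takes no account of how many maps were made.

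**Working it through.** **1. The two lists side by side**

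| Region | Protocol section 2 (Aim 3) and 6b | SAP Aim 3 |
|---|---|---|
| vmPFC | named | named |
| Ventral striatum | named | absent |
| VTA | named | absent |
| Salience network | absent | named, nodes not listed |

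The shared set has one region, and the union has four. A direction is stated for the protocol's regions (enhanced). None is stated for the salience network.

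**2. The plan's own threshold.** The 0.999 quantile of Student's t is 3.24 at about 57 degrees of freedom. The stated T therefore reproduces as a one-sided p of 0.001; a two-sided p of 0.001 would need about 3.47. This is a voxel-level cut within a map and says nothing about the number of maps. The SAP's sample-size figure concerns physical activity and is not an input here.

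**3. Error per map.** Under the global null every detected cluster is false, so the false discovery rate equals the chance of at least one detected cluster. Each map then has a 0.05 chance of a false-positive result.

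**4. Error across k seed maps.** With independent maps and one contrast per seed, the chance of at least one false-positive map is 1 − 0.95^k:

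- k = 1 (one main test): 0.0500, or 5%.
- k = 2 (SAP list): 1 − 0.9025 = 0.0975, or 9.75%.
- k = 3 (protocol regions, if each is used as a seed): 1 − 0.8574 = 0.1426, or 14.3%.
- k = 4 (union): 1 − 0.8145 = 0.1855, or 18.5%.

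**5. Allowing for correlation.** The maps share participants and outcome, so independence is unlikely. The documents give no correlation between maps, so the values below are assumptions. They come from a simulation of 1,000,000 draws of equally correlated two-sided normal tests, each at 0.05.

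| Assumed correlation | 2 maps | 3 maps | 4 maps |
|---|---|---|---|
| 0 | 9.8% | 14.3% | 18.6% |
| 0.3 | 9.5% | 13.6% | 17.4% |
| 0.5 | 9.1% | 12.6% | 15.6% |
| 0.8 | 7.8% | 9.8% | 11.4% |

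The row at zero agrees with the formula to within simulation error. Counting the salience network as one seed may understate k, since its nodes are not listed.

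**The case against.** The strongest reply is that this is a secondary aim in a study that protocol section 2 calls a pilot. Neither document promises family-wise control for imaging, so correcting across every seed would impose a standard that the plan never claimed. That stands. It argues against a mandatory Bonferroni level and leaves the primary test untouched. It does not excuse two different a-priori lists.

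Some stronger readings are tempting, but the documents do not support them:

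- *The SAP no longer tests the reward-valuation hypothesis.* Section 6b states that hypothesis as connectivity between the reward regions and vmPFC, with a whole-brain threshold. A vmPFC seed map still covers the ventral striatum and VTA as targets. What is lost is their status as a-priori regions in the SAP.
- *Aim 3 cannot be confirmed or refuted.* vmPFC is in both documents, so a result there can be judged under either.
- *The salience analysis has no hypothesis at all.* Protocol hypothesis 3 expects baseline network connectivity to predict change in activity. It is broad enough to cover a network predictor, but gives no specific salience hypothesis or direction.
- *The false-positive chance is about 34%.* That is 1 − 0.95^8 = 33.7%. It needs four seeds in both resting-state and task data, all independent. Both data types are mentioned, but nowhere is that eight-map grid planned.

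It is also fair to say that neither document plans the four-seed family. The 18.5% describes what happens if both lists are run, and correlation would lower it.

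**Conclusion.** The contradiction holds and should be corrected. Protocol and SAP share only vmPFC as an a-priori region, no main seed or contrast is named, and the stated cluster threshold acts map by map. The chance of at least one false-positive seed map is up to twice nominal under the SAP's list, nearly three times under the protocol's, and between two and four times if all four are run. These multiples rest on the global null, one contrast per seed, the salience network counted as one seed, and a correlation between maps that the documents do not give.

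Confidence is high for the mismatch and the missing rule across seeds, and lower for the exact percentages. The consequence is limited to how Aim 3 imaging findings outside vmPFC can be interpreted.

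**What to change.** Before imaging is linked to the activity outcomes:

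1. Put one identical region list in protocol section 2 (Aim 3), protocol section 6b and SAP Aim 3, restoring the ventral striatum and VTA to the SAP as a-priori regions.
2. Name vmPFC-to-ventral striatum/VTA connectivity as the single main seed-based test, at the threshold already stated. It is the contrast for which section 6b gives both a hypothesis and a direction. Say which data carry it, since Aim 3 mentions both task and resting-state imaging and a single test needs one source.
3. Label the salience network exploratory, or state its nodes, hypothesis and direction.
4. Leave modularity where it is. It is pre-specified as hypothesis 2, and the seed mismatch gives no reason to demote it.

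The cost is wording in two documents, with no new data or participants. The downside is that a positive result in any other seed can be reported only as exploratory. The alternative is to keep several seeds as formal tests and divide the cluster level among them: 0.05/2 = 0.025, 0.05/3 = 0.0167 or 0.05/4 = 0.0125. That also holds the error at 5% or below, but costs power in every map, which a single main test avoids.

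### Aim 3 labels a within-person rise in activity as treatment response, but specifies neither the arms analysed nor a marker-by-arm contrast

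*SAP*

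**What the plan says.** Protocol Section 2, Aim 3, defines the outcome as "successful behavioural change (i.e., increased physical activity post-intervention versus baseline", a comparison of each participant with their own earlier week. The same paragraph states the question as "whether and what neuromarkers predict successful behavioural change as a function of the intervention". Hypothesis 3 is more neutral: "Individual differences in structural and functional network connectivity at baseline will predict change in physical activity".

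The SAP's Aim 3 paragraph aims to "predict successful behavior change at the single subject level in older adults at risk for AD". Its stated purpose for the models is "to identify the brain networks that predict treatment response (physical activity engagement) at an individual level". The tools named for this, besides machine learning, are "independent linear regression models using leave-one-out cross validation (LOOCV) and bootstrap resampling". It gives no change score, cut-off, arm or analysis set.

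Protocol Section 6b says of the imaging work: "To answer questions about the intervention effect and prediction of behavioural change, both a priori ROI seed-based analyses of functional connectivity are performed". It calls these analyses secondary. The group-by-time interaction in that section belongs to the mixed models for the activity outcomes, and no counterpart is written for the brain markers.

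Hypothesis 2 reads "Enhanced brain network modularity at baseline will predict exercise-related executive function gains". Section 6b schedules the neuropsychological battery at T1, T2 and T3.

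**The concern.** Response to an intervention means the difference the intervention makes. Change from one's own baseline also contains whatever would have happened without it. Such change is plausible here. Section 3.2 admits only people who want to be more active, Section 4.1 describes a control condition that is itself monitored daily, and Section 5.1 takes baseline from a single week.

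A marker that predicts who becomes more active under either condition could therefore be published as predicting who responds to social motivation. Section 2 gives messaging tailored to a person's neurobehavioural profile as the ultimate goal, and the SAP expects generalisable single-subject values. For that use the distinction matters: a general predictor of change does not say who should receive the intervention.

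Hypothesis 2 has a parallel problem. Executive gains after repeated testing may include practice effects shared by both arms, and nothing in the plan removes these before the gains are called exercise-related.

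**Working it through.** **1. The plan's own figure.** The only sample-size figure is the SAP's for the two-arm activity comparison: difference 10.0%, SD 14.0%, 80% power, two-sided 0.05, 30 per arm.
- n per arm = 2 × (1.960 + 0.842)² × (14/10)² = 2 × 7.85 × 1.96 = 30.8, so 31 per arm and 62 in total, against 60 stated.
- Power at 30 per arm = Φ(10 / (14 × √(2/30)) − 1.960) = Φ(0.806) = 79.0%.

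The figure reproduces to within rounding. Aim 3 has no sample-size statement.

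**2. What each possible model estimates.** Let C be activity change (or week-4 activity given baseline), G the arm (0 control, 1 intervention) and M a baseline brain marker:

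C = b0 + b1·G + b2·M + b3·M·G

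The marker's slope is b2 in controls and b2 + b3 in the intervention arm. Response to the intervention that depends on the marker is b3.
- Intervention arm only: the model estimates b2 + b3.
- Both arms pooled 1:1 with no interaction, and equal marker spread in the arms: the model estimates the average, (b2 + b2 + b3)/2 = b2 + b3/2.
- Both arms with the interaction: b3 is estimated directly.

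If b3 = 0 and b2 ≠ 0, the first two models find a predictor although nothing about the intervention has been predicted. Leave-one-out validation does not help. It guards against overfitting, and b2 will validate as well as b3.

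**3. Is the interaction written anywhere?** Protocol Section 2 (Aim 2) does ask whether motivational and decision-making traits moderate the intervention effect, so the idea is present for those measures. For brain markers no such term appears in Section 2 (Aim 3), in Section 6b or in SAP Aim 3. The example covariates for the imaging analysis in Section 6b include neither arm nor baseline activity.

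**4. Precision of the missing contrast.** Power of 80% and two-sided 0.05 are borrowed from the SAP's primary calculation. I use Fisher's z and assume a control-arm correlation of 0, no drop-out and no allowance for testing several markers.
- Between arms: z difference = 2.802 × √(2/(n − 3)) and r = tanh(z).
  - 30 per arm: 2.802 × √(2/27) = 0.76, r = 0.64.
  - 60 per arm: 2.802 × √(2/57) = 0.52, r = 0.48.
- Plain correlation, no arm contrast: r = tanh(2.802/√(N − 3)), giving 0.49 for N = 30, 0.36 for N = 60 and 0.25 for N = 120.

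Both arm sizes are shown because the SAP plans 60 participants and protocol Section 4.1 plans 120.

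**The case against.** **Controls are not excluded.** A reader might infer that Aim 3 ignores the control arm. The documents do not say that. They are silent on the analysis set, and both the Aim 3 question and the imaging paragraph of Section 6b mention the intervention. This stands. The gap is the missing contrast, and pooling both arms without it would not close that gap.

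**No responder cut-off is planned.** A reader might take the SAP's 10% and 14%, assume no mean change in controls, and compute that 50% of controls and Φ(10/14) = 76% of the intervention arm rise, so that about two thirds of responders (0.500/0.762 = 66%) would have risen anyway. The documents do not support this. They plan linear regression with no cut-off at zero and do not say that 14% is the SD of change. The 66% is also an upper bound: the two shares allow an overlap as small as 0.500 + 0.762 − 1 = 0.262, which gives 34%. And the calculation contains no marker.

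**Regression to the mean is a weak explanation here.** Sections 2 and 5.5 say that the imaging was already collected in PREVENT-AD (the SAP's wording is looser). Chance variation in the baseline accelerometer week should be nearly unrelated to an earlier scan. This largely stands. Season and monitoring matter only if the marker predicts them, which the documents cannot show.

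**Baseline adjustment has its own artefact.** Suppose a marker relates only to stable activity and nothing truly changes. Its partial correlation with follow-up given a noisy baseline is ρ(1 − r)/√((1 − ρ²)(1 − r²)). For assumed marker–activity correlations ρ of 0.3 to 0.5 and baseline–follow-up correlations r of 0.5 to 0.9, this runs from 0.07 to 0.33, where the change score gives zero. This stands for arm-independent associations. Randomisation protects the interaction.

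**Status and feasibility.** The imaging analyses are secondary, the protocol calls the study a pilot, and Hypothesis 3 already uses neutral wording. Individual treatment effects are unobserved, so a whole-brain model of them cannot be cross-validated directly. All true, and reasons to limit the claim.

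**Hypothesis 2.** Shared practice gains distort the modularity association only if modularity predicts practice, and the test list is in an attachment not available here. So practice is a possibility, not a finding.

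**Conclusion.** The point holds as a mismatch between the stated conclusion and the stated analysis. The outcome is within-person change, the label is treatment response, and for brain markers nothing written separates the two, whichever arms are used. This follows from the text and the algebra and needs no assumed figures.

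The documents do not show how large the error would be, nor that any particular marker would be misread. The detectable correlations of 0.64 and 0.48 describe the cost of the remedy and rest on the assumptions in step 4 of the working. The plan should be corrected before the imaging analyses are run. The primary comparison of activity between arms is unaffected.

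**What to change.** In SAP Aim 3 and protocol Section 6b:

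1. State that both randomised arms are included in the prediction analyses.
2. For the a priori seed and ROI regressions, model week-4 activity on baseline activity, group, marker and marker-by-group. Reserve the phrase *predicts treatment response* for the interaction.
3. Report whole-brain and leave-one-out predictors, and any association not contrasted between arms, as *predicts activity change*. Note that baseline adjustment does not protect these from measurement-error artefacts. Cross-validation can stay as planned.
4. For Hypothesis 2, apply the same contrast (modularity-by-group on T3 executive function, adjusted for baseline) before calling gains exercise-related.
5. Reconcile the planned sample size (60 or 120), since it sets the precision of the interaction.

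The cost is SAP wording, one extra term in the seed regressions and narrower labels elsewhere; no new data are needed. The real price is precision: with 30 per arm only a large difference between arms would be detectable, so fewer markers will qualify. If the team judges the interaction too imprecise to report, using the *activity change* label throughout costs nothing and is accurate.
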